4.3 Subject Exclusion Criteria

- Established diagnosis of diabetes mellitus, use of anti-diabetes medications, or a Hgb A1C of >7.0%
- History of eating disorder, uncontrolled mood or thought disorder, significant gastrointestinal disorder or malabsorption, or significant hepatic or renal impairment
- 3. Current use of medical therapy for overweight/obesity including phentermine, orlistat, lorcaserin, naltrexone/bupropion, and liraglutide or history of weight loss surgery. Concomitant use of medications with side effects known to potentially influence appetite are allowed if on a stable dose for at least 12 months
- 4. History of symptomatic hypoglycemia.
- 5. Use of systemic glucocorticoids (stable dose daily inhaled corticosteroid allowed)
- 6. Chronic viral hepatitis C; subjects with a history of hepatitis C successfully treated can enroll >12 months after sustained virologic response
- 7. Alcohol or substance use disorder in the past year as defined by DSM-V or positive urine drug screen
- 8. Current pregnancy, actively seeking to become pregnant or breastfeeding

 Any serious health or other condition which, in the opinion of the PI or their designee, could potentially interfere with the ability of a subject to comply with the procedures and assessments of the protocol or to safely participate and complete the study.

Co-enrollment Guidelines: Co-enrollment in other trials is restricted, other than enrollment on observational studies. Study staff should be notified of co-enrollment as it may require the approval of the PI.

4.4 Justification for Exclusion of Special Populations

Exclusion of Pregnant and/or Breastfeeding Women:

- Pregnancy: Pregnant women are excluded from this study because the effects
 of ICR on the developing human fetus are unknown. Additionally, the metabolic
 changes associated with pregnancy could would confound assessment of the
 effects of diet intervention.
- **Breastfeeding:** Nursing mothers are excluded from study participation because the nutritional needs of nursing mothers require stable caloric intake and the potential risk of maternal intermittent fasting nursing is unknown.

Exclusion of Subjects <18 years of age: Persons age <18 years are excluded from this study because there are insufficient data regarding the risk of ICR in adults to judge the potential risk in growing children and young adults.

Exclusion of Subjects >65 years of age: Persons age >65 are excluded from this study because there are insufficient data regarding the risk of ICR in adults <65 years of age to judge the potential risk in aging adults. Additionally, changes in body composition and resting metabolic rate independent of weight change, occur with advanced age and could potentially confound study measures [42].

Exclusion of Subjects Who Cannot Provide Informed Consent: To ensure compliance with study-mandated diet and lifestyle, subjects must be able to provide initial and ongoing informed consent to participate in this study.

5 Study Interventions

5.1 Assessment of Subject Compliance with Study Intervention(s)

Subjects will be asked to keep a daily diary, which will record how well they complied with their assigned diet as well as their daily step count. Subjects in the ICR arm will be asked to indicate which days they restrict calories. These diaries will be reviewed with the study team at all study visits.

5.2 Concomitant Medications and Procedures

All concomitant medications, including prescription, over-the-counter, and non-prescription medications will be recorded.

5.3 Prohibited Medications and Procedures

During study participation, subjects may not initiate medical therapy or undergo surgical intervention intended to promote weight loss. Any change in medications, including supplement and vitamin use, or proposed surgical intervention should be discussed with the study team.

6 Study Schedule and Procedures

6.1 Screening

The following procedures will be performed at the NIH Clinical Center to determine if a subject is eligible for study participation and are expected to be completed over 2 visits:

- 1. History and physical exam and vital signs including measurement of blood pressure, height, and weight
- Blood collection for laboratory assessments including acute care, hepatic, and mineral panels, Hgb A1c, fasting glucose and insulin, fasting lipid profile, complete blood counts, CRP, HIV viral load, CD4+ T-cell count, and hepatitis serologies
- 3. Urine studies including urinalysis, urine protein/creatinine ratio and albumin/creatinine ratio, and urine drug screen
- 4. Blood or urine pregnancy testing for women of childbearing potential
- 5. Nutrition consultation for body composition measurements including weight, and waist and hip circumference. Subjects will also receive instructions on completion of 3-day food diary.
- 6. Receive a pedometer and instruction on its use to assess daily activity level
- 7. 1-day trial of the very low-calorie diet (approximately 25% of estimated needs) to assess ability and motivation to lose weight through ICR

6.2 Baseline Assessments

Prior to randomization, subjects will undergo baseline assessments to include:

- Additional laboratory studies including fasting glucose and insulin (for HOMA-IR), lipid panel, CRP, leptin, ghrelin, peptide YY (PYY), BDNF, urine ketones, and inflammatory biomarkers
- Oral glucose tolerance test (OGTT)
- 3. Indirect calorimetry (REE)
- Nutrition consultation for review of 3-day food diary and counseling on the AHA
 diet and caloric restriction. Subjects will also receive information on
 recommended physical activity and ways to increase daily steps.
- 5. Questionnaires:
 - a. Three-factor eating questionnaire (TFEQ) [43]

- b. Symptoms Review Questionnaire
- c. Beck Depression Inventory II
- d. RAND Medical Outcomes Study 36-Item (SF-36; quality of life)
- e. Positive and Negative Affect Schedule (PANAS)
- f. Modified visual analog scales (eg, mood, hunger)
- 6. DXA
- 7. Blood or urine pregnancy testing for women of childbearing potential
- 8. Transient elastography with controlled attenuation parameter (CAP) (Fibroscan®, Echosens, Paris, France)

Baseline assessments may be completed over multiple visits within 4 weeks of randomization.

6.3 Randomization (Day 0)

Study subjects will be randomized sequentially to the ICR arm or the observation arm.

All subjects will receive dietary counseling consistent with the AHA diet recommendations, physical activity recommendations for healthy lifestyle, and a pedometer. Subjects randomized to the 2-5 ICR group will implement the AHA diet 5 days per week, and on 2 non-consecutive days per week, will consume approximately 25% of estimated caloric need in the form of supplemental beverages or small meals. Subjects randomized to the standard-of-care group will receive the AHA dietary guidelines, which will include healthy food selection, portion size control, education on caloric goals for healthy weight management, physical activity recommendations, and pedometers, but not instruction on intermittent fasting.

6.4 Study Phase (Weeks 1-12)

Interim safety visits will be scheduled for weeks 1, 4, 8, and 12. Subjects will visit the NIH Clinical Center as outpatients. The following assessments and procedures will occur:

- 1. Vital signs including weight and blood pressure
- 2. Physical exam and interval medical history at weeks 4, 8, and 12
- 3. Fasting blood collection for acute care, hepatic, and mineral panels, insulin, glucose and lipids, and CRP, as well as serum, plasma, and PBMCs for storage at weeks 4, 8 and 12. Hgb A1C at week 12. Leptin, ghrelin, PYY, BDNF, inflammatory markers, urine ketones and HIV viral load will be repeated at weeks 4, 8, and 12.
- 4. Nutrition consultation at weeks 4 and 12: Completion of 3-day food diary and waist and hip measurements at weeks 4 and 12
- Review of subject diary documenting compliance and daily steps at weeks 1, 4,
 and 12

- 6. Symptoms Review Questionnaire at weeks 1, 4, 8 and 12
- 7. TFEQ at weeks 4, 8, and 12
- 8. Modified visual analog scales at week 12
- 9. At week 12, baseline assessments will be repeated. Assessments include:
 - Beck Depression Inventory, RAND SF-36, and PANAS questionnaires
 - REE
 - OGTT
 - DXA
 - Blood or urine pregnancy testing for women of childbearing potential
 - Transient elastography with CAP (Fibroscan®, Echosens, Paris, France)

Study visit windows are as follows: Week 1: +/-3 days, Weeks 4, 8, and 12: +/- 7 days.

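### No pregnancy test is listed between baseline and week 12, so an unsuspected pregnancy could stay on the fasting diet; tests at day 0 and weeks 4 and 8 are a cheap safeguard

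*Combined protocol and SAP*

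**What the plan says.** Section 4.3 excludes "Current pregnancy, actively seeking to become pregnant or breastfeeding". Section 4.4 gives as one reason that the effects "of ICR on the developing human fetus are unknown"; the other is that pregnancy would confound the diet comparison. Sections 6.7 and 11.5 stop participation and caloric restriction when a pregnancy occurs.

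The same item, "Blood or urine pregnancy testing for women of childbearing potential", is listed at four points:

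- screening (6.1);
- baseline (6.2), where "Baseline assessments may be completed over multiple visits within 4 weeks of randomization", and nothing ties the test to day 0;
- week 12 (6.4), in the list that opens "At week 12, baseline assessments will be repeated. Assessments include";
- week 24 (6.5).

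It is not listed at day 0 (6.3) or among the procedures for weeks 1, 4 and 8 (6.4).

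Other contacts exist during the diet. Section 6.4 lists "Physical exam and interval medical history at weeks 4, 8, and 12" and "Symptoms Review Questionnaire at weeks 1, 4, 8 and 12". Section 7 places interval history at every visit after screening, and Appendix A lists history and physical at week 1 as well. Section 11.2 requires adverse-event questioning at each contact.

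Women in the ICR arm, "on 2 non-consecutive days per week, will consume approximately 25% of estimated caloric need" (6.3). Control women do not fast.

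**The concern.** A rule that stops the diet in pregnancy protects a fetus only once the pregnancy is known. After baseline, the first scheduled test comes at week 12, when the diet is over or nearly over. If a woman in the ICR arm conceives shortly before or soon after randomization and does not suspect it, no scheduled test would show it while stopping could still spare much exposure. What is at stake is avoidable exposure to an intervention whose fetal effects the protocol itself calls unknown. This concerns the ICR arm only.

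**Working it through.** The plan gives no figure on this point, so the check compares the procedure lists and works out the timing.

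**Inputs from the protocol.** The diet lasts 12 weeks (84 days) with 2 restricted days a week. Baseline may be up to 28 days before randomization. Weeks 4, 8 and 12 each have a window of 7 days either way, so they fall on days 21–35, 49–63 and 77–91.

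**Assumptions not in the protocol.** The diet ends on day 84 unless stated otherwise. A test turns positive L = 10 to 14 days after conception. For the means only, conceptions are spread evenly over days 0–84 and no pregnancy is recognised by other means.

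**Current schedule**

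- Gap between the baseline and week-12 tests: 84 days if baseline is tested on day 0; 84 + 28 = 112 days if tested 4 weeks earlier; 112 + 7 = 119 days with a late week-12 visit.
- Worst-case exposure (conception at or before day 0, no recognition, full adherence): 2 × 12 = 24 restricted days. It is 2 × 11 = 22 if week 12 falls on day 77, and 2 × 13 = 26 if the diet continues to a visit on day 91.
- Mean for conceptions during the diet: 84 / 2 = 42 days, or 42 × 2/7 = 12 restricted days.

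**With tests at day 0 and weeks 4 and 8**

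- Nominal interval between tests: 28 days. Longest intervals with windows: 35 − 0 = 35, 63 − 21 = 42 and 91 − 49 = 42 days.
- Exposure can exceed the interval because of the lag. Nominal worst case: 28 + L = 38 to 42 days; × 2/7 = 10.9 to 12.0 restricted days. With windows: 42 + L = 52 to 56 days; × 2/7 = 14.9 to 16.0 restricted days.
- Mean, L = 10. Conceptions on days 0–18 are found at day 28, those on days 18–46 at day 56, and later ones run to day 84: (18 × 19 + 28 × 24 + 38 × 19) / 84 = 1736 / 84 = 20.7 days, or 5.9 restricted days.
- Mean, L = 14: (14 × 21 + 28 × 28 + 42 × 21) / 84 = 1960 / 84 = 23.3 days, or 6.7 restricted days.
- Conceptions before day 0: if the baseline test was 28 days old, a day-0 test finds conceptions from 28 further days and takes them from as many as 24 restricted days to none. Conceptions too recent to show on day 0 would be found at week 4, after 28 days on diet (35 if that visit is late): 8 to 10 restricted days.

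**Number of pregnancies.** The documents do not give the number of women of childbearing potential. Purely as an illustration, 2 to 10 such women in the ICR arm and 2% to 10% conceiving per year give 2 × 0.02 × 12/52 = 0.009 to 10 × 0.10 × 12/52 = 0.23 over the 12 weeks.

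**The case against.** The strongest case against acting is that the plan already has reasonable protection. Two tests precede randomization, and women seeking pregnancy are excluded. Interval history reaches week 1 under section 7 and Appendix A. Adverse events are asked about at every contact. The stop rule acts on a pregnancy known from any source, including self-report. The intervention is reduced intake on two days a week, few pregnancies are expected, and nothing in the protocol sets a testing interval that the schedule breaches.

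Most of this stands, and it limits the point. It does not remove it. The entry exclusion acts only at entry. History, examination and questioning depend on someone having reason to suspect pregnancy. None of the listed items of the Symptoms Review Questionnaire concerns pregnancy or menses. Section 8.1 expects lethargy and irritability from the diet itself, so such symptoms have a ready alternative explanation.

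A reader might infer three stronger things, none of which the documents support:

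- That the plan contradicts itself. The exclusion and stop rules are coherent without interim tests; they simply have no scheduled test behind them for most of the diet.
- That there is no contraception or missed-period advice. The listed eligibility criteria contain no contraception requirement, but the consent pages were not available, so nothing can be said about advice given there.
- That added testing would halve fetal exposure. The fall in the mean from 42 to about 21–23 days holds only if nobody's pregnancy is recognised in any other way. Any recognition through history or self-report narrows it.

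**Conclusion.** The point holds as a low-cost improvement in participant safety. From baseline to week 12 no pregnancy test is scheduled, and the existing contacts would not reliably find an early, unsuspected pregnancy. The worst-case figures require conception at or before day 0, no recognition and full adherence; later conceptions mean less exposure. The gain in mean exposure is an upper bound under the stated assumptions of even conception and a 10 to 14 day lag. Added testing shortens exposure but does not abolish it. Fetal harm is unknown, not shown. Power, type I error and the trial's conclusions are not in question.

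**What to change.** - **Section 6.3:** require a negative pregnancy test on day 0, before randomization, for women of childbearing potential. The baseline test may be done that day to meet this.
- **Section 6.4:** add the protocol's existing blood or urine pregnancy test at weeks 4 and 8, run on the urine already collected for ketones.
- **Both arms:** section 6.7 stops participation for pregnancy regardless of arm, and section 4.4 also names confounding.

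The cost is a line of wording in each section and up to three tests per woman, all at visits already planned. Day 0 needs one urine sample unless the baseline test is moved there; weeks 4 and 8 need no new sample. The protocol gives no prices, so calling the tests inexpensive is a judgement. The downsides are tests in control women who have no fasting exposure, a few more positive results to handle, and a rare earlier withdrawal that would bring replacement under section 11.8.

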6.5 Final Follow-up Visit (Week 24)

After completing the 12-week randomized portion of the study, subjects will be followed for an additional 12 weeks during which time they will not be instructed to follow any specific dietary pattern. Both groups' visits will occur at week 24. (+/- 4 weeks)

The following procedures will be performed:

- 1. Vital signs including weight and blood pressure
- 2. Physical exam and interval medical history
- 3. Fasting blood collection for acute care, hepatic, and mineral panels, Hgb A1C, insulin, glucose and lipids, as well as serum, plasma, PBMCs for storage
- 4. Symptoms Review Questionnaire
- 5. Modified visual analogue scale
- 6. Transient elastography with CAP
- 7. 3-day food diary and anthropometric measurements
- 8. REE
- 9. DXA scan
- 10. Blood or urine pregnancy testing for women of childbearing potential

6.6 Early Termination Visit

If a subject's participation is terminated before completing the study, then they will be asked to return to the NIH Clinical Center for a Termination Visit. Laboratory tests and study evaluations to be conducted at that visit will be determined on the basis of the subject's health, their willingness, and the appropriateness of the test at that time point.

6.7 Pregnancy and Follow-up Visit

If a subject becomes pregnant during the course of participation, then her participation in the study will be stopped and she will be counseled to discuss diet and nutrition with her obstetrician. The study team will request that the subject notify the team of the pregnancy outcome.

7 Study Procedures/Evaluations

History and Physical Examination

The **initial history**, performed at the screening visit, will consist of a comprehensive review of the subject's medical history, including any previous surgical procedures and any previous significant medical conditions. A comprehensive review of systems will also be performed. A detailed medication history will be taken. Allergies and all current medications will be recorded. **Interval history**, performed at all subsequent visits, will consist of questioning subjects about any new medical issues or any noted changes in health. The most recent medication list will be reviewed with subjects to assess for any changes in dosing, new medications, or medication discontinuation. **Physical examination** will consist of a review of vital signs as well as examination of general appearance (visualization), heart (auscultation), lungs (auscultation), abdomen (palpation and auscultation), and extremities (visualization and palpation). Additional elements of the physical examination may be performed at the investigator's discretion.

Blood Draw

To assess clinical safety parameters, as well as research measures, blood will be drawn at time points listed above.

Table 2. Venipuncture Volumes for Subjects

	Screen	Baseli ne	Week 1	Week 4	Week 8	Week 12	Week 24
Day +/- Window	-1 to 1	1 ± 1	3 ± 1	5 ±1	8 ± 1	11 ± 1	29 + 6
Safety hematology, chemistry and OGTT tests	X 26mL	X 22mL		X 19mL	X 19mL	X 32mL ²	X ³ 22mL ²
Blood for Serum	X 8mL	X 16mL		X 16mL	X 16mL	X 16mL	X 16mL
Blood for Plasma	X 12mL			X 12mL	X 12mL	X 12mL	X 12mL
Blood for PBL Storage		20mL		20mL	20mL	20mL	20mL
Total volume	46mL	58mL		67mL	67mL	80mL	70mL
Total for all study visits							388mL

Pedometer

To assess activity at baseline and the impact of the diet intervention on activity, subjects will use a pedometer to record daily steps. This will be recorded on a patient diary and reviewed by the study staff at clinic visits.

Transient Elastography and CAP

Liver stiffness will be determined using transient elastography [44] and hepatic fat content estimated by CAP. At least ten measurements will be made using the M-probe according to the manufacturer's recommendations and the median will be expressed in kilopascal (kPa) units. If measurements from the M-probe are unsuccessful at the baseline assessment, the XL probe may be used at the operator's discretion. Use of the XL probe at baseline will be noted, and the XL probe will also be used for subsequent assessment of that subject.

Whole Body DXA will be performed to determine total body and regional percent fat, lean body mass, and bone density. The technique has a precision error (1 SD) of 3% for fat and 1.5% for lean body mass [45]. Trunk, extremity, and trunk-to-extremity ratio will also be assessed [46, 47].

REE

REE is measured by indirect calorimetry. Following at least a 4-hour fast, a large plastic cover or "bubble" is placed over the subject's head while a plastic sheet covers the subject's upper body to prevent external air from entering the bubble. Oxygen flows into the bubble through a valve at the top. The calorimeter measures the amount of oxygen (O_2) consumed and the amount of carbon dioxide (CO_2) produced while at rest by comparing the concentrations of O_2 and CO_2 in the air inspired by the subject with the concentration in the air expired by the subject. The modified Weir equation is used to convert the volume of O_2 consumed and the volume of CO_2 produced per minute into a value for REE expressed in calories [48].

Genetic Analysis

PBMCs will be stored and analyzed for single nucleotide polymorphisms that may affect metabolism and immunology.

OGTT

75-g OGTT will be performed with sampling for insulin and glucose at 0, 30, 60, and 120 min.

Nutritional Analysis

A 3-day food record, completed at baseline and weeks 4 and 12, will be analyzed for protein, carbohydrate, fat, micronutrient, and alcohol intake (Nutrition Data Systems).

Anthropometric Measurements

Measurements of waist-to-hip ratio will be performed using a standardized technique [49].

TFEQ and Modified Visual Analog Scale

The TFEQ will be administered to measure three aspects of eating attitudes: cognitive restraint of eating, disinhibition, and hunger [50]. Modified visual analog scales (VAS) will be used to assess subjective hunger and satiety three times a day the days prior to week 0 and week 12 assessments [51, 52]. VAS assesses 'desire to eat,' 'hunger', 'fullness,' and 'prospective consumption.'.

PANAS

Subjects will report on Likert scales how they feel emotionally. The PANAS is a common index of emotional state [53].

Symptoms Review Questionnaire

Subjects will report on Likert scales their mood, level of energy, difficulty concentrating, headaches, feeling cold, constipation, negative emotions (depression, anxiety, irritability), hunger, and preoccupation with food for the week prior to the visit.

RAND SF-36 scale

This questionnaire gauges physical and psychosocial effects of the dietary interventions. It has been used as a quality of life assessment in previous studies of ICR [30].

7.1 Return of Research Results

Any clinically relevant test results will be shared with the subject throughout the study. Results of research procedures or evaluations (including incidental findings) will be shared with participants if they are medically actionable. Such results will be discussed with the participant along with guidance for appropriate follow-up with their healthcare provider. Any findings discovered beyond the completion of the primary research will not be returned.

8 Potential Risks and Benefits

8.1 Potential Risks

Blood Draw. Collection of blood may be associated with discomfort, bruising, local hematoma formation and, on rare occasions, infections, lightheadedness, and fainting. The amount of blood drawn for research purposes will be within the limits allowed for adult subjects by the NIH CC (Medical Administrative Policy 95-9: Guidelines for Limits of Blood Drawn for Research Purposes in the Clinical Center: http://cc-internal.cc.nih.gov/policies/PDF/M95-9.pdf.

Pedometer. No risks are associated with pedometer use and it is associated with minimal inconvenience.

OGTT. No serious risks are associated with the OGTT. Some subjects experience temporary abdominal discomfort after drinking the sugar solution. If the results of an OGTT demonstrate glucose intolerance or insulin resistance, recommendations will be made for appropriate follow-up monitoring and management.

REE. Subjects may experience claustrophobia during the measurements.

Transient elastography. There are no foreseeable risks associated with this non-invasive procedure.

DXA. Subjects will be exposed to radiation from three DXA scans, for total estimated effective dose in 1 year of 0.00007 rem. This is considered a low exposure. The risk of this exposure is too low to be reliably measured.

Caloric restriction. [29, 30, 57, 58] In previous studies of ICR, no serious adverse events (SAEs) occurred. In the study by Harvie et al., a 6-month trial, 8% of subjects on the 2-5 ICR regimen reported physical symptoms including lack of energy, headaches, feeling cold, and constipation. Minor psychological symptoms were reported in 15% of the 2-5 ICR group, including lack of concentration, bad temper, and a preoccupation with food. These adverse effects abated after caloric restriction was stopped [29, 30]. Conversely, 6% of 2-5 ICR subjects reported better health and increased energy [30]. Furthermore, 32% of 2-5 ICR had increased self-confidence and positive mood. Overall, a minority of subjects (9-15%) would be expected to develop minor physical and psychological AEs related to 2-5 ICR. Such AEs include lethargy, feeling cold, difficulty concentrating, and irritability. Study subjects will be counseled on potential side effects and will record symptoms in the diet and symptom diary.

